### **Intervention group:**

Intervention: ABC4D with RT-CGM for 6 months

Visit 2: CGM review and intervention study start

- Attend 4 weeks after visit 1
- Remove CGM, upload data to DiaSend/Dexcom Studio software (subject can do upload the data at home prior to attending the visit) and review data with subject.
- Adjust ICR, ISF and basal rates if deemed necessary based on CGM data.
- Initialize CBR algorithm case base with 3 standard cases (breakfast, lunch and dinner) using subjects existing ICR
- Switch on the ABC4D device
- Instructions to subjects to ensure:
  - Capillary blood glucose measurements fasting, pre-meals and pre-bed.
  - Accurate subject input of pre-meal capillary blood glucose, carbohydrate (CHO) amount (g), alcohol (none/<2units/>2units), pre- or post-meal exercise (none/moderate/intense), type of meal absorption (fast/medium/slow), illness (yes/no), stress (none/mild/severe), menstrual cycle and insulin given if CBR algorithm advice not taken
  - Calibration of the CGM every 12 hours and sensor change every 7 days as per manufacturer's instructions
  - No correction boluses for 2 hours post-meal unless clinically indicated (CBG >15mM or ketosis)
- A detailed ABC4D user guide will be given to the subject

Follow-up clinic visits at 1 month, 3 months and 6 months:

### **Visit 3**

Review at 1 month:

- Review of subject's diabetes control including insulin requirements, incidence of hypoglycaemia, exercise, driving etc.

### **Visit 4**

Review at 3 months:

- Review of subject's diabetes control including insulin requirements, incidence of hypoglycaemia, exercise, driving etc.
- Random venous blood taken for HbA1c
- Weight (kg)

### Visit 5

Review at 6 months:

- Review of subject's diabetes control including insulin requirements, incidence of hypoglycaemia, exercise, driving etc.
- Random venous blood taken for HbA1c
- Weight (kg)
- Questionnaires to be completed

### ABC4D case base revision and adaptation

The ABC4D case base will be revised every two weeks throughout the study and this will be a semi-automatic process for the first 25 participants entered into the study if allocated to the intervention group. For the remaining 155 participants, if allocated to the intervention group, the revisions will be fully automated requiring minimal manual input. The adaptation summary will be approved and the case-base updated by the study team. This provides remote supervision and prevents any potential system faults despite safety measures. The subjects will not need to attend the clinical research unit for the ABC4D revisions.

### Control group:

Intervention: Standard care for 6 months

### Visit 2: CGM review and control study start

- Attend 4 weeks after visit 1
- Remove CGM, upload data to DiaSend/Dexcom Studio software (subject can do upload the data at home prior to attending the visit) and review data with subject.
- Adjust ICR, ISF and basal rates if deemed necessary based on CGM data.

Follow-up clinic visits at 1 month, 3 months and 6 months:

### Visit 3

Review at 1 month:

- Review of subject's diabetes control including insulin requirements, incidence of hypoglycaemia, exercise, driving etc.

### Visit 4

Review at 3 months:

- Review of subject's diabetes control including insulin requirements, incidence of hypoglycaemia, exercise, driving etc.
- Random venous blood taken for HbA1c
- Weight (kg)

### Visit 5

Review at 6 months:

- Review of subject's diabetes control including insulin requirements, incidence of hypoglycaemia, exercise, driving etc.
- Random venous blood taken for HbA1c
- Weight (kg)
- PAID score questionnaire and acceptability questionnaire to be completed

Usual care will be maintained for diabetes throughout the study. No concomitant medical therapies are contra-indicated, except GLP-1 analogues, SLGT2 inhibitors and gliptins. Support will be offered to any participants who have concerns about their diabetes management.

Subjects in the intervention group using the ABC4D will have the opportunity to call a physician for medical support and an engineer for technical support 24 hours a day throughout the study.

*Statistics* This is a randomised study with an intervention group and a control group. Outcomes from the study are absolutes as described above. 142 subjects with T1DM, are required to demonstrate an HbA1c difference of 0.6% with  $\alpha$  of 0.05 and 90% power (two-tailed). We aim to screen n=160 and randomise n=80 in each group. This power calculation is based on using a population mean HbA1c of 7.9% with a standard deviation of 1.1.

The sample size is comparable to other technology transfer studies, is a realistic number for recruitment and provides robust clinical validation and safety date of a new technology.

[figure not shown]
Missing, unused, and spurious data will be assessed on an individual basis and may be ignored, withdrawn or the visit may be removed from the analysis with appropriate justification adjudicated by the Principal Investigator.

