### **Clinical review at 1 month, 3 months and 6 months:**

*Review at 1 month (coincides with visit 4):*

- Review of subject's diabetes control including insulin requirements, incidence of hypoglycaemia, exercise, driving etc.

*Review at 3 months (coincides with visit 6):*

- Review of subject's diabetes control including insulin requirements, incidence of hypoglycaemia, exercise, driving etc.
- Random venous blood taken for HbA1c
- Weight (kg)

*Review at 6 months (coincides with visit 8):*

- Review of subject's diabetes control including insulin requirements, incidence of hypoglycaemia, exercise, driving etc.
- Random venous blood taken for HbA1c
- Weight (kg)
- PAID score, DQOL and DTSQ questionnaires to be completed

Usual care will be maintained for diabetes throughout the study. No concomitant medical therapies are contra-indicated, except GLP-1 analogues, SGLT2 inhibitors and gliptins. Support will be offered to any participants who have concerns about their diabetes management.

Subjects in the intervention group using the ABC4D will have the opportunity to call a physician for medical support and an engineer for technical support 24 hours a day throughout the study.

**Statistics** This is a randomised study with an intervention group and a control group. Outcomes from the study are absolutes as described above. 142 subjects with T1DM, are required to demonstrate an HbA1c difference of 0.6% with  $\alpha$  of 0.05 and 90% power (two-tailed). We aim to screen n=160 and randomise n=80 in each group. This power calculation is based on using a population mean HbA1c of 7.9% with a standard deviation of 1.1.

The sample size is comparable to other technology transfer studies, is a realistic number for recruitment and provides robust clinical validation and safety date of a new technology.

[figure not shown]
Missing, unused, and spurious data will be assessed on an individual basis and may be ignored, withdrawn or the visit may be removed from the analysis with appropriate justification adjudicated by the Principal Investigator.

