**Secondary outcomes:**

HbA1c at 3 months  
Post-prandial AUC at 4 hours and 6 hours  
Post-prandial AUC (<3.9) at 4 hours and 6 hours  
Episodes of hypoglycaemia within 4- and 6-hours post-prandially  
% time in target glucose (3.9-10mmol/l)  
% time in hypo- (<3.9mmol/l) and hyperglycaemia (>10mmol/l)  
Glycaemic risk: LBGI and HBGI  
Glycaemic variability: MAGE and CONGA-2  
Change in weight (kg)  
Number achieving target HbA1c (≤ 53 mmol/mol)  
24-hours insulin dose requirements  
PAID score questionnaire  
DQOL questionnaire  
DTSQ Questionnaire  
Acceptability questionnaire (non-validated)

These are validated, published metrics.

**Timescale:** Each subject will be in the study for 6 months. It is anticipated that it will take 15 months to complete the 4th phase.

**Population:** 142 subjects with T1DM, are required to demonstrate an HbA1c difference of 0.6% with  $\alpha$  of 0.05 and 90% power (two-tailed). We aim to screen n=180 and randomise n=90 in each group. This power calculation is based on using a population mean HbA1c of 7.9% with a standard deviation of 1.1.

The first 25 participants will be randomised to either the ABC4D running in semi-automatic mode (where the revisions are done using a semi-automatic process-see page 23) or a standard bolus calculator. The remaining participants will be randomised to either the fully automated ABC4D (where revisions are fully automated) or a standard bolus calculator. Screening 180 participants will ensure that at least 142 participants are included to enable demonstration of a significant difference between the fully automated ABC4D system and a standard bolus calculator.

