**Visit 1: Screening**

- Attend the clinical research unit
- Routine clinical examination
- ECG
- Non-fasting venous blood taken for HbA1c, creatinine, lipids.
- Urine for albumin/creatinine ratio
- Urine pregnancy test in female subjects of childbearing age
- CHO counting and hypoglycaemia education revision by a qualified health care professional.
- The basal insulin dose, insulin:carbohydrate ratio (ICR) and insulin sensitivity factor (ISF) will be reviewed and adjusted if needed.
- PAID score, DQOL and DTSQ questionnaire to be completed
- Real-time continuous glucose monitor (Dexcom) placed in the anterior abdominal wall according to manufacturer's instructions.
- Subjects will be shown how to insert the sensor themselves, interpret the CGM data in real time and to set the hypo- and hyperglycaemia threshold alarms. The alarm threshold will be set at 4mmol/l and 11mmol/l and subjects will be encouraged to keep it at those levels and not to reduce the hypoglycaemia threshold below 3.3mmol/L.
- Subjects to complete a 4-week run-in period using RT-CGM (Dexcom) to familiarize themselves with the RT-CGM and for optimization of treatment prior to study start
- Instructions to subjects to ensure:

- Capillary blood glucose measurements fasting, pre-meals and pre-bed.
- Calibration of the CGM every 12 hours and sensor change every 7 days as per manufacturer's instructions (a copy will be given to subjects)
- Food diaries and physical activity record to be kept for the 4-week run-in period

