**Table: Overview of activities at each visit for subjects in the intervention group**

Activity / Visit no	1	2	3	4	5	Additional information
Insertion of CGM sensor	x					Subjects will change the sensor every week at home throughout the study (24 weeks)
Removal of CGM sensor					x	
Food diary	x					
CGM review with subject		x				
Initialise CBR algorithm and ABC4D start		x				
Update CBR algorithm with new cases					x	This will be done automatically with remote supervision every 1 week throughout the study

Clinical examination	X					
Weight measurement	X			X	X	
Venous blood test	X			X	X	
Urine test	X					
Pregnancy test	X					
ECG	X					
Questionnaire/s	X					
Follow-up clinical review		X	X	X	X	

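### Phase 4 schedules no 6-month DQOL or DTSQ for the control arm, so as written these two listed secondary outcomes cannot be compared between arms

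*Combined protocol and SAP*

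**What the plan says.** The Phase 4 list of secondary outcomes includes "DQOL questionnaire" and "DTSQ Questionnaire", alongside PAID and a non-validated acceptability questionnaire. None of the four is tied to one arm or to a time point.

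At Phase 4, Visit 1: Screening, which precedes the randomisation section and applies to every subject, the instruction is "PAID score, DQOL and DTSQ questionnaire to be completed".

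At 6 months the two arms have different text. For controls (Phase 4, Control group, Visit 5) it is "PAID score questionnaire and acceptability questionnaire to be completed". For the intervention group (Phase 4, Intervention group, Visit 5) it is "Questionnaires to be completed", with no instrument named. The Phase 4 activity table, titled "Overview of activities at each visit for subjects in the intervention group", has a row "Questionnaire/s" that is marked under Visit 1 and blank under Visit 5. There is no corresponding table for controls.

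In Phase 3, by contrast, the control arm's 6-month review reads "PAID score, DQOL and DTSQ questionnaires to be completed". The Phase 3 intervention arm has the same three instruments plus acceptability at 6 months.

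**The concern.** Phase 4 exists to compare ABC4D with a standard bolus calculator when both arms wear real-time CGM. A patient-reported outcome serves that purpose only if it is measured after randomisation in both arms. The control line is a complete instruction naming two instruments, and staff who follow it will give those two. DQOL and DTSQ would then exist for controls only at screening.

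What would remain for these two outcomes is, at best, a before-and-after change in the intervention arm. That change cannot be attributed to ABC4D. The baseline is taken at Visit 1, before a 4-week run-in on real-time CGM that is also meant for optimising treatment, and 6 months of real-time CGM follow. Any effect of CGM, of treatment adjustment or of extra clinical contact would be mixed with the effect of the bolus calculator. The control arm is there to separate these, and its values would be absent.

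**Working it through.** The plan gives no sample size, hypothesis or analysis for DQOL or DTSQ, so there is no figure of its own to reproduce on this point. The check is to set each place where questionnaires are mentioned against the outcome list.

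| Place in the protocol | Who | When | PAID | DQOL | DTSQ | Acceptability |
|---|---|---|---|---|---|---|
| Phase 4, Secondary outcomes | no restriction | not stated | listed | listed | listed | listed |
| Phase 4, Visit 1: Screening | everyone | baseline | yes | yes | yes | not named |
| Phase 4, Intervention group, Visit 5 | intervention | 6 months | unspecified | unspecified | unspecified | unspecified |
| Phase 4 activity table, Visit 5 column | intervention | 6 months | no mark | no mark | no mark | no mark |
| Phase 4, Control group, Visit 5 | control | 6 months | yes | **no** | **no** | yes |
| Phase 3, Intervention group, 6-month review | intervention | 6 months | yes | yes | yes | yes |
| Phase 3, Control group, 6-month review | control | 6 months | yes | yes | yes | not named |

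**Control arm.** The 1-month and 3-month reviews (Visits 3 and 4) mention no questionnaires. Scheduled DQOL or DTSQ assessments after screening therefore number 0 + 0 + 0 = 0 over Visits 3, 4 and 5. The planned arm size is 90 in the Phase 4 Population paragraph and 80 in the Phase 4 Statistics paragraph. Either way, the number of controls with a scheduled follow-up value is 0 of 80 or 0 of 90, which is 0%.

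**Intervention arm.** There is at most one follow-up assessment, at Visit 5, if the unspecific Visit 5 text is read as covering the listed instruments. If the table is followed instead, there is none for any questionnaire.

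**What can be compared.** A between-arm contrast needs follow-up values in both arms. For DQOL and DTSQ the control side is empty, so both the difference at 6 months and the difference in change from baseline are undefined. Imputation does not help, because a whole arm lacks the outcome by design and there are no observed control values to model. PAID can still be compared if the intervention Visit 5 text is read naturally. It cannot if the table is followed.

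**Is the blank table cell just a convention?** No. The Phase 3 table marks questionnaires at both the first and the last visit (1 and 16). In the Phase 4 table, other 6-month activities such as weight and venous blood do carry a mark at Visit 5.

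**Effect on the primary outcome.** None. For context, the Phase 4 sample size reproduces from its stated inputs: n per arm = 2 × (1.960 + 1.282)² × 1.1² / 0.6² = 70.6, rounded up to 71, or 142 in total as stated.

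**The case against.** The best reply is that this is a drafting omission and not a decision. The outcome list carries both instruments without restriction, everyone completes them at screening, Phase 3 names them in both arms at 6 months, and nothing in the protocol gives a reason for dropping them. Staff may well give all three in practice. That reading is probably right, but it does not remove the problem. The visit schedule is what staff work from, and the control line is explicit.

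Two narrower objections stand in part. The intervention Visit 5 text is unspecific, but it does not contradict the outcome list. The firm conflicts are between the control Visit 5 line and the outcome list, and between the intervention table and the intervention Visit 5 text. Also, the loss of all intervention-arm follow-up requires an overview table to override an explicit visit instruction, so it is a conditional worst case. The table is not reliable elsewhere either: it gives weekly case-base updates where the section on case base revision gives two-weekly ones. The size of the problem should therefore be judged on the control arm, with the table as a related correction.

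Finally, these are two of many secondary outcomes and have no stated power or analysis. That limits the importance of the point but does not answer it.

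**Conclusion.** The concern holds. If the Phase 4 schedule is followed as written, two of the three validated questionnaires (two of the four listed) have no follow-up value in any control participant, 0 of 80 to 90, and no between-arm comparison of them can be made. If the intervention table were followed over the visit text, the intervention arm would have no follow-up questionnaire at all. That second consequence is conditional.

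The conclusion assumes that staff follow the written control Visit 5 line and that no document outside the protocol adds the missing instruments. It does not touch HbA1c, its sample size or the CGM outcomes. It should be corrected, because the data cannot be collected retrospectively.

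**What to change.** Use the same wording at Visit 5 in both Phase 4 arms, naming PAID, DQOL and DTSQ. State explicitly which arms complete the acceptability questionnaire. It is a listed secondary outcome, but at present it is named at 6 months for controls only. Add a mark under Visit 5 in the questionnaire row of the intervention table. It would also help to give the 6-month time point for these questionnaires in the outcome list.

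If the intention really was to drop DQOL and DTSQ in Phase 4, remove them from the secondary outcomes and say so.

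The cost is three wording edits to the schedule and a few minutes of participant time at a visit already planned, with instruments already used at screening. If any controls have passed Visit 5 when the change is made, report how many lack DQOL and DTSQ for this reason.

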**Trial Objectives, Purpose and Design:** The principal research objectives are to assess the safety, technical proof of concept and efficacy of the ABC4D device in subjects with T1DM. Safety will be assessed by measuring post-prandial glucose for hypo- and hyperglycaemia. This will initially be assessed over 8 hours with two meal challenges, in a controlled clinical environment. Phase 2 will take place over 6 weeks where subjects will be using the ABC4D for bolus calculations in their normal environment. Subjects will have blinded CGM (Enlite sensor, iPro2, Medtronic) throughout the study and the data will be downloaded every week allowing the research team to update the algorithm's case base with new cases from the preceding week. The algorithm will have the capacity to retrieve new cases in an automatic process, but for safety the research team will accept each case manually in phase 1 and 2. The primary outcome in the third and final phase of the study is the change in HbA1c after subjects have used the ABC4D for 6 months. In the 3rd phase of the study, the subjects will have 4 weeks of consecutive CGM, followed by one week of blinded retrospective CGM each month for the remainder time of the study. The CGM data will be downloaded and calibrated retrospectively, allowing the researcher to update the algorithm's case base with new cases on a monthly basis. In phase 3 and phase 4 the retrieval of new cases derived from combined CGM data and data from the ABC4D application will be a semi-automatic process without the research team approving each case. However, the research team will approve the revision summary before updating the case-base.

The final phase (Phase 4) will aim to investigate the efficacy of ABC4D with RT-CGM compared to standard bolus calculator (defined as the bolus wizard within insulin pumps, bolus calculator in glucose meter or the ABC4D app as a standard bolus calculator (without CBR adaptation)) with RT-CGM where the primary outcome is HbA1c at 6 months. RT-CGM will be used throughout the study period in both the intervention and control group.

The study will be conducted over four phases as outlined below:

## Phase 1

**Objective:** To demonstrate safety and technical proof of concept of the ABC4D in a controlled clinical environment

**Methodology** Non-randomised open label study

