**Primary outcome:**

HbA1c at 6 months

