**Subject inclusion criteria:**

- Adults ≥18 years of age
- Diagnosis of T1DM for > 1 year
- On MDI using a basal-bolus insulin regime or continuous subcutaneous insulin infusion (insulin pump)
- Structured education
- HbA1c ≥ 48mmol/mol and ≤ 86mmol/mol
- No severe hypoglycaemia (defined as needing 3rd party assistance) in previous year

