**Recruitment**

Recruiting will be undertaken in the diabetes clinics at Imperial College Healthcare NHS Trust, from registered research databases and from interested subjects who contact us. Participant information sheets will be given to potential subjects and, after a minimum of 48 hours and following any questions, informed consent will be taken.

*Subjects who have already participated in phase 1 and/or 2 of the study can also be recruited for phase 3 and they will be re-consented. These subjects will not need re-screening, however they may need to repeat 1 week of CGM using iPRO2 for initializing of the ABC4D at the start of the Phase 3 study, this is at the discretion of the Principal Investigator.*

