**Visit 1: Screening**

- Attend the clinical research unit
- Routine clinical examination
- ECG
- Non-fasting venous blood taken for HbA1c, creatinine, lipids.
- Urine for albumin/creatinine ratio
- Urine pregnancy test in female subjects of childbearing age
- CHO counting and hypoglycaemia education revision by a qualified health care professional.
- The basal insulin dose will be reviewed and adjusted if needed.
- Questionnaires to be completed
- Continuous glucose monitor (CGM retrospective/blinded iPro2, Medtronic or Dexcom) placed in the anterior abdominal wall according to manufacturer's instructions. CGM sensor to be worn for 6-7 continuous days.
- Instructions to subjects to ensure:
  - Capillary blood glucose measurements fasting, pre-meals, post-meals and pre-bed.
  - Food diaries and physical activity record to be kept for 6 days

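### Phases 3 and 4 name no primary analysis model; pre-specifying adjustment for Visit 1 HbA1c would gain precision at almost no cost

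*Combined protocol and SAP*

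**What the plan says.** - **Primary outcome.** Phases 3 and 4 both list "HbA1c at 6 months".
- **Statistics paragraphs, Phases 3 and 4.** Each says "Outcomes from the study are absolutes as described above" and sizes the trial for a difference of 0.6, two-sided 5%, 90% power, using a "population mean HbA1c of 7.9% with a standard deviation of 1.1". The result is 142 in total. Neither paragraph, nor any other part of the document, names a test, model or covariate for the primary comparison.
- **Planned numbers.** Both Statistics paragraphs give 80 per arm. The Phase 4 Population paragraph gives 90 per arm, and the Phase 4 section on case base revision agrees with it (25 + 155 = 180).
- **Baseline HbA1c.** Visit 1 in both phases includes "Non-fasting venous blood taken for HbA1c, creatinine, lipids". Its only evident use is eligibility: "HbA1c ≥ 48mmol/mol and ≤ 86mmol/mol".
- **Phase 4 timing.** After the Visit 1 sample, "Subjects to complete a 4-week run-in period using RT-CGM", partly to optimise treatment. The Phase 4 visit table shows no blood test at Visit 2.
- **Phase 3 only.** Trial Objectives, Purpose and Design describes the Phase 3 primary outcome as "the change in HbA1c after subjects have used the ABC4D for 6 months". Phase 3 Recruitment says of people from earlier phases, "These subjects will not need re-screening", while the section on potential risks and benefits describes a venous blood test at the start of every phase without naming HbA1c.

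**The concern.** In a randomised comparison of HbA1c, the baseline value of the same measurement is usually the most useful covariate. Here it is collected anyway, but the plan never says whether it enters the analysis. If the final values are compared without it, the confidence interval is wider and the power lower than the data allow.

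The model is also left open in two open-label trials, where it could be chosen after the data are seen. The Phase 3 wording adds a smaller ambiguity, since an unadjusted change score and a final value have different variances and therefore different power.

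**Working it through.** **1. The plan's own figure.** Inputs from the Statistics paragraphs: difference 0.6, SD 1.1, two-sided 5%, 90% power, 1:1 allocation.

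n per arm = 2 × ((1.95996 + 1.28155) × 1.1 / 0.6)² = 70.63, so 71 per arm and 142 in total. This matches exactly, with no baseline correlation and no change-score SD.

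**2. What adjustment would give.** With correlation r between Visit 1 and 6-month HbA1c, the ANCOVA residual SD is 1.1 × √(1 − r²): 1.094, 1.049, 0.953 and 0.786 at r = 0.1, 0.3, 0.5 and 0.7. The documents give no r, so these are assumptions. Power is from the noncentral t with 2n − 2 degrees of freedom (2n − 3 for ANCOVA). The 95% CI half-width is t × SD × √(2/n). For example, with n = 71 unadjusted it is 1.977 × 1.1 × √(2/71) = 0.365.

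| Analysed | Unadjusted | r = 0.1 | r = 0.3 | r = 0.5 | r = 0.7 |
|---|---|---|---|---|---|
| 71 per arm: power | 89.8% | 90.0% | 92.3% | 96.1% | 99.5% |
| 71 per arm: half-width | 0.365 | 0.363 | 0.348 | 0.316 | 0.261 |
| 80 per arm: power | 92.9% | 93.1% | 94.9% | 97.7% | 99.8% |
| 80 per arm: half-width | 0.344 | 0.342 | 0.328 | 0.298 | 0.245 |
| 90 per arm: power | 95.3% | 95.5% | 96.8% | 98.8% | 99.9% |
| 90 per arm: half-width | 0.324 | 0.322 | 0.309 | 0.280 | 0.231 |

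(The unadjusted 89.8% at 71 per arm is the t-test value; the normal approximation behind 142 gives 90.1%.)

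Estimating one slope inflates the variance by about 1/138 = 0.7% at N = 142. The table leaves this out. It matters only at r = 0.1, where the variance reduction is r² = 1% and the two analyses are practically equal.

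**3. Phase 3 change score, if analysed unadjusted.** Its SD is √(s² + 1.1² − 2 × r × s × 1.1), where s is the baseline SD. The documents do not give s, so two values are used: 1.1, and 0.84. The second is a normal distribution with mean 7.9 and SD 1.1, truncated to an entry range assumed to be about 6.5% to 10.0%.

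- At r = 0.3 the change SD is 1.302 (s = 1.1) or 1.167 (s = 0.84). Power with 142 is 77.9% or 86.1%.
- Power with 142 falls below 90% when r is under about 0.50 (s = 1.1) or 0.39 (s = 0.84). With 80 per arm the thresholds are about 0.44 and 0.30.

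If the change is instead analysed by ANCOVA with baseline as covariate, the treatment estimate is identical to that for the final value, so this ambiguity has no numerical effect.

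**4. People who may lack a current baseline.** At most 6 + 20 = 26 participants from Phases 1 and 2 could enter Phase 3 without re-screening. Phase 4 requires re-screening, so the question does not arise there.

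**The case against.** A reader might infer that the plan has chosen an unadjusted analysis and excluded baseline HbA1c from it. The documents do not go that far. The sentence about absolutes also stands in the Statistics paragraphs of the single-arm Phases 1 and 2, so it may be carried-over text, and it says nothing about covariates. Reproducing 142 from a raw SD shows how the trial was sized, and that is compatible with a later adjusted analysis. What is established is that the model is unspecified. This objection stands and limits the point.

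Nor is there an error in the sample size. The 142 is right for an unadjusted comparison, and randomisation makes that comparison unbiased.

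The gain may also be small. The entry window narrows the baseline range, and in Phase 4 the baseline precedes a run-in with treatment optimisation; both could lower r. At 90 per arm the unadjusted power is already 95.3%, and r = 0.3 lifts it only to 96.8%. That stands too, and it is why no single gain is claimed. It is not a reason to omit the adjustment, because at r = 0.1 essentially nothing is lost.

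Finally, the change-score figures should not be read as a forecast for Phase 3. They require that the single phrase in the objectives is followed, that the change is analysed unadjusted, and that r is low. The Phase 3 outcome list and Statistics paragraph point to the 6-month value instead.

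**Conclusion.** The point holds as a gap in pre-specification and a missed gain in precision. Phases 3 and 4 name no primary analysis model, the stated outcome and sizing are consistent with an unadjusted comparison of final values, and the Visit 1 HbA1c is given no stated role in the analysis. No bias and no error in the 142 follow from this.

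The size rests on an assumed r. With 142 analysed, r = 0.5 narrows the interval by about 13% (0.365 to 0.316), r = 0.3 by about 5% (to 0.348), and r = 0.1 hardly at all. The power gain shrinks as the number analysed rises to 80 or 90 per arm, though the proportional narrowing of the interval is the same. The outcome wording and the re-screening question are secondary and confined to Phase 3. This is a free improvement.

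**What to change.** In the Statistics paragraphs of Phases 3 and 4, keep the existing sentence for the secondary outcomes and add:

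> The primary analysis compares 6-month HbA1c between randomised arms by ANCOVA adjusted for Visit 1 HbA1c, two-sided 5%, reported with a 95% CI; a missing baseline value is handled by mean imputation or a missing indicator so that no randomised participant is dropped for it.

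Choose one of the two missing-baseline methods in advance. The sample size should not be cut in anticipation of the gain, because r is unknown.

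In Phase 4, also state whether the first 25 participants, whose intervention arm uses the semi-automatic mode, are in this comparison, and reconcile 80 per arm (Statistics) with 90 per arm (Population). The two questions are linked: without those 25, a total of 160 leaves 135, below 142, and a total of 180 leaves 155.

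In Phase 3, align the outcome wording in Trial Objectives, Purpose and Design with the Phase 3 primary outcome. Reconcile the Recruitment waiver with the blood test described under potential risks and benefits, so that re-enrolled participants have a current baseline HbA1c.

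The cost is wording only, with no new visits or participants. If the waiver is now applied without an HbA1c, it adds one test for each of at most 26 people.

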### ***Randomisation***

Subjects who fit the inclusion criteria will be randomized to either ABC4D (intervention group) or standard care (control group) in a 1:1 ratio. Both groups will be using RT-CGM.

Standard care is defined as the bolus wizard within insulin pumps, bolus calculator in glucose meter or the ABC4D app as a standard bolus calculator (without CBR adaptation).

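### Phase 4 gives two enrolment targets, 180 and 160; read with the plan's 25-participant first stage, 160 leaves 135 against the 142 required

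*Combined protocol and SAP*

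**What the plan says.** The Phase 4 target appears in three places in the combined protocol and SAP.

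- **Phase 4, Population** (below the secondary outcomes): "We aim to screen n=180 and randomise n=90 in each group". The paragraph then divides the phase in two: "The first 25 participants will be randomised to either the ABC4D running in semi-automatic mode" or a standard bolus calculator, and after that "The remaining participants will be randomised to either the fully automated ABC4D (where revisions are fully automated) or a standard bolus calculator". It justifies the total as follows: "Screening 180 participants will ensure that at least 142 participants are included to enable demonstration of a significant difference between the fully automated" system and a standard bolus calculator.
- **ABC4D case base revision and adaptation**: fully automated revision applies as follows: "For the remaining 155 participants, if allocated to the intervention group".
- **Phase 4, Statistics** (after the control-group visits): "142 subjects with T1DM, are required to demonstrate an HbA1c difference of 0.6% with" a two-sided alpha of 0.05 and 90% power, using an SD of 1.1. Then: "We aim to screen n=160 and randomise n=80 in each group". This paragraph does not mention the 25-participant stage.

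The required number (142) and its inputs are the same in both Phase 4 paragraphs. The 160 sentence also appears, in identical words, in the Population and Statistics paragraphs of Phase 3, which has no such stage.

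**The concern.** One phase has two totals, 20 participants apart, and no rule says which governs. Someone who takes the target from the Statistics paragraph alone would stop at 160. If the split in the Population paragraph is also applied, the comparison to which that paragraph attaches the 142 would then fall below 142 before anyone is lost to follow-up.

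A related looseness affects both totals. Each paragraph sets the number screened equal to the number randomised (180 = 2 × 90; 160 = 2 × 80), yet the Phase 4 Randomisation section admits only those who qualify: "Subjects who fit the inclusion criteria will be randomized to either ABC4D" or standard care. The assurance that screening 180 secures the 142 therefore assumes no screen failures.

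**Working it through.** **Inputs.** Difference 0.6, SD 1.1, two-sided alpha 0.05, power 90% (Phase 4 Statistics); 1:1 allocation (Phase 4 Randomisation); first stage of 25 (Phase 4 Population). The plan names no formula. The check uses the normal approximation for two means, which returns the plan's figure, with noncentral-t results beside it.

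**Step 1: reproduce the 142.**

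n per group = 2 × (1.960 + 1.2816)² × 1.1² / 0.6² = 70.6, rounded up to 71, so 142 in total. This matches the plan.

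**Step 2: which total fits the rest of the text.**

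- 180 − 25 = 155, the number in the case base revision section.
- 160 − 25 = 135, which appears nowhere.

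**Step 3: apply the 142 to the fully automated comparison.** If only participants after the first 25 count:

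- Needed: 142 + 25 = 167 randomised.
- 180 − 167 = 13 to spare. The tolerable loss is 13/155 = 8.4%.
- 160 − 167 = −7, so 135 remain.

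**Step 4: power.** Power ≈ Φ(0.6 / (1.1 × √(1/n₁ + 1/n₂)) − 1.960), unadjusted comparison, no loss. For example, 67 v 68 gives √(1/67 + 1/68) = 0.1721, then 0.6 / (1.1 × 0.1721) = 3.169, and Φ(1.209) = 88.7%.

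| Reading | Groups | Normal | Noncentral t |
|---|---|---|---|
| Plan's requirement, 142 | 71 v 71 | 90.1% | 89.8% |
| 160, after first 25 only | 67 v 68 | 88.7% | 88.2% |
| 180, after first 25 only | 77 v 78 | 92.4% | 92.1% |
| 160, early controls added | 67–68 v 80 | 90.9–91.1% | 90.5–90.7% |
| 180, early controls added | 77–78 v 90 | 94.0–94.1% | 93.7–93.9% |
| 160, split ignored | 80 v 80 | 93.2% | 92.9% |

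The rows with early controls added assume that the first 25 divide 12/13. With 160 randomised, the fully automated arm is then 80 − 13 = 67 or 80 − 12 = 68.

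**Step 5: with loss.** The documents give no loss rate. At an assumed 5% to 20%, power (normal) runs from about 87.0% to 80.9% starting from 135, and from 91.1% to 85.9% starting from 155.

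**The case against.** The figure of 135 joins two paragraphs that may never have been meant together. The Statistics paragraph has no split, and on its own terms 160 exceeds 142 (93.2% power). The Population paragraph has the split but uses 180. If the 160 is a leftover from Phase 3, nobody planned a comparison on 135.

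Both stages also share the same comparator, so counting standard-calculator participants from the first 25 as controls is a natural reading, and 160 then still exceeds 90%. The Phase 4 objective and Randomisation section do not distinguish the two ABC4D modes at all. Even the worst case without loss costs about 1.5 points of power, and a careful reader can recover 180.

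Most of this stands, and it limits the weight of the point: the shortfall is conditional and small. It does not remove the contradiction, because two different totals are in the current text whichever reading is taken. Nor does it settle the comparison. The Population paragraph names the fully automated system as the one the 142 is for, and no passage says that early controls are pooled.

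**Conclusion.** The point holds. The Phase 4 Statistics paragraph contradicts both the Population paragraph and the case base revision section on the number to be randomised: 160 against 180. The evidence favours 180. That the 160 was carried over from Phase 3 is an inference, though the identical wording supports it.

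The shortfall of 7, and the power of 88.7% instead of 90.1%, rest on three conditions: 160 is the operative total, the 25-participant stage applies, and early controls are not counted. If early controls are counted, or the split is ignored, 160 meets the 90% target. The plan's own calculation of 142 is correct. The text should be fixed, but the design does not need to change.

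**What to change.** - In the Phase 4 Statistics paragraph, replace the 160 and 80 per group with 180 randomised, 90 per group, to agree with the other two places.
- In both Phase 4 paragraphs, give the number screened and the number randomised separately.
- State that the 142 refers to the fully automated comparison after the first 25 participants, and whether standard-calculator participants among those 25 enter it as controls.
- Replace the assurance about 180 with the margin it gives: 155 against 142, so 13 (8.4%) can be lost if early controls are not counted. Set the sponsor's expected loss rate beside it.

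The cost is a wording amendment to two paragraphs. Nobody is added beyond the 90 per group already in the Population paragraph. More than 180 need be screened only if some of those screened are not randomised.
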